8.1 Description

This study will be conducted as a multi-centre, parallel group, wait list design clinical trial testing the reduction of acute severe respiratory events requiring workforce removal in HCW with OM85. Health Care Workers who are eligible will receive daily OM85 for 3 months. Group 1 “Wait-list group” will be given daily OM85 for 3 months commencing in Month 3, with 3 months follow-up off treatment. Group 2 “Initial treatment group” will be given daily OM85 for 3 months commencing in on day 0, with 3 months follow-up off treatment

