10.2 Scheduled visits

This study consists of 5 visits (Group 1 - WLC) or 4 visits (Group 2 – initial treatment) over 6 or 9 months respectively (see Figure 1) Study procedures to be performed at each visit are detailed in the Schedule of Assessments and Procedures in Appendix 1.

Visits should be conducted within the specified visit windows where possible.

Figure 1: Study timeline and procedures. Nasal swab collection (blue arrow), blood collection (red arrow).

Group 1 (WLC)

Visit 1 – Screening and randomisation

The following assessments and procedures will be performed and recorded at this visit:

- Obtain written informed consent
- Evaluate inclusion and exclusion criteria
- Obtain demographic history
- Obtain medical history
- Vital signs
- Explain daily respiratory symptom data collection and assist with collection for Day 0

Once all screening procedures have been completed and eligibility confirmed, the participant will be registered with the Sponsor. Further information on the registration process is provided in the Study Reference Manual.

Visit 2: Treatment initiation 3 months post randomisation (±5 days)

- Update demographic & medical history
- Vital signs

- Nasal swab
- Collection of blood samples
- Dispense study medication and explain administration
- Adverse event assessment

Visit 3: Treatment cessation 6 months post randomisation (± 5 days)

- Vital signs
- Nasal swab
- Collection of blood samples
- Clarify any missing data (daily respiratory symptoms) with participant, if not previously addressed by email/SMS
- Adverse event assessment
- Collect used investigational product packaging and unused investigational product

Visit 4: Follow up cessation 9 months post randomisation (± 5 days)

- Vital signs
- Nasal swab
- Collection of blood samples
- Clarify any missing data (daily respiratory symptoms) with participant, if not previously addressed by email/SMS
- Adverse event assessment

Unscheduled Visit: at time of ARI necessitating workforce removal

- Vital signs
- Nasal swab
- Collection of blood samples
- Clarify any missing data (daily respiratory symptoms) with participant, if not previously addressed by email/SMS
- Adverse event assessment

Group 2 (Initial Treatment)

Visit 1 – Screening, randomisation, and treatment initiation

The following assessments and procedures will be performed and recorded at this visit:

- Obtain written informed consent
- Evaluate inclusion and exclusion criteria
- Obtain demographic history

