- Obtain medical history
- Vital signs
- Nasal swab
- Collection of blood samples
- Drug delivery
- Dispense study medication and explain administration
- Explain daily respiratory symptom data collection and assist with collection for Day 0

- Adverse event assessment

Once all screening procedures have been completed and eligibility confirmed, the participant will be registered with the Sponsor. Further information on the registration process is provided in the Study Reference Manual.

Visit 2: Treatment cessation 3 months post randomisation (± 5 days)

- Vital signs
- Nasal swab
- Collection of blood samples
- Clarify any missing data (daily respiratory symptoms) with participant, if not previously addressed by email/SMS
- Adverse event assessment
- Collect used investigational product packaging and unused investigational product

Visit 3: Follow up cessation 6 months post randomisation (± 5 days)

- Vital signs
- Nasal swab
- Collection of blood samples
- Clarify any missing data (daily respiratory symptoms) with participant, if not previously addressed by email/SMS
- Adverse event assessment

Unscheduled Visit: at time of ARI necessitating workforce removal

- Vital signs
- Nasal swab
- Collection of blood samples
- Clarify any missing data (daily respiratory symptoms) with participant, if not previously addressed by email/SMS
- Adverse event assessment

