13.2.1 Analysis sample

All participants randomised who receive at least one dose of study treatment will be included in the "intention-to-treat" group for statistical analyses.

Participants who complete the treatment period and take at least 80% of scheduled doses will be included in the "per protocol" group for statistical analyses.

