13.2.2 Statistical analyses

The *interim analysis*, undertaken at month 1 on both the "intention-to-treat" and "per protocol" groups, will examine the primary outcome: if the treatment difference is statistically significant in favour of OM85 the DSMB will consider immediately switching WLC participants to OM85.

Between-group differences in the primary outcome at 3 months will be assessed using log-binomial regression. Secondary outcomes measured to follow-up cessation will be assessed using mixed-effects models with group and stage (treatment/follow-up) (main effects and interaction) as fixed effects and HCW as random effect. Time-to-ARI analyses will use the log-rank test. Analyses will be undertaken on both the "intention-to-treat" and "per protocol" groups.

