13.3.2 Secondary efficacy endpoints and mechanistic endpoints

The secondary endpoints, defined in Section 7.2.2, and mechanistic evaluations, defined in Section 7.2.3, will be assessed using mixed-effects models with group and stage (treatment/follow-up) (main effects and interaction) as fixed effects and HCW as random effect. Time-to-ARI, including LRI, analyses will use the log-rank test.

These analyses will be undertaken, on both the “intention-to-treat” and “per protocol” groups, regardless of the outcome of the primary endpoint analysis.

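### The secondary-endpoint model does not tie stage to months, and on the visit labels none of its coefficients compares treated with concurrent never-treated workers

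*Combined protocol and SAP*

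**What the plan says.** Section 13.2.2 states: "Secondary outcomes measured to follow-up cessation will be assessed using mixed-effects models with group and stage (treatment/follow-up"), with main effects and interaction as fixed effects and worker as a random effect. Section 13.3.2 repeats this for the secondary and mechanistic endpoints, which "will be assessed using mixed-effects models with group and stage (treatment/follow-up) (main effects and interaction"). Time-to-event endpoints go to the log-rank test instead. Neither section gives dates for the two stages.

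The visit labels run on each arm's own clock.
- **Group 1 (wait-list).** Section 8.1 says this arm "will be given daily OM85 for 3 months commencing in Month 3, with 3 months follow-up off treatment". Section 10.2 lists "Visit 2: Treatment initiation 3 months post randomisation", "Visit 3: Treatment cessation 6 months post randomisation" and "Visit 4: Follow up cessation 9 months post randomisation".
- **Group 2 (initial treatment).** Section 10.2 lists "Visit 2: Treatment cessation 3 months post randomisation", with follow-up cessation at 6 months. Appendix 1 puts that last visit at Day 120.

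Section 13.3 schedules endpoint analyses at 3 months and at study completion. Section 13.3.1 gives the primary endpoint a window that closes before Group 1 starts OM85, analysed by log-binomial regression. No month-3 model is given for the non-time-to-event secondary endpoints.

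On the analysis set, Section 13.2.1 says: "All participants randomised who receive at least one dose of study treatment will be included" in the intention-to-treat group.

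**The concern.** A wait-list design has one randomised, concurrent, drug-versus-no-drug contrast: months 0-3. If stage follows the visit labels, the mixed model leaves that period out for Group 1. Its group terms then compare on-drug with on-drug, or off-drug with off-drug, in different quarters of a pandemic. A shift in background risk could make an inert drug look helpful or harmful. With flat risk, the group and interaction terms would show nothing even if OM85 worked.

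ARI at 3 months has its own concurrent model as the primary. The exposure is therefore mainly the LRI proportions, symptom days and COV endpoints.

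**Working it through.** **1. The plan's own figure.** Section 13.2 gives 80% power for 20% versus 13.5% with 500 per group. I use a two-proportion test, pooled standard error under the null, two-sided 0.05 (sidedness is not stated in the plan):

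power = Φ[(|p1 − p2| − 1.96·s0)/s1], with s0 = √(2p̄(1 − p̄)/n) and s1 = √((p1(1 − p1) + p2(1 − p2))/n).

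Here s0 = 0.02362 and s1 = 0.02353, so (0.065 − 0.04629)/0.02353 = 0.795 and power is 78.7%, close to the stated 80%. For 20% versus 15% with 1000 per group it is 83.8%. The same formula serves below.

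**2. What the model cells contain on the visit labels.**

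| Cell | Months | Status |
|---|---|---|
| Group 2, treatment | 0-3 | on OM85 |
| Group 2, follow-up | 3-6 | previously treated |
| Group 1, treatment | 3-6 | on OM85 |
| Group 1, follow-up | 6-9 | previously treated |
| none | Group 1, 0-3 | never treated |

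The group term at either stage compares the same drug status in different quarters. The stage term compares on with after, in fixed order. The one concurrent pairing, Group 1 treatment with Group 2 follow-up, is not a model coefficient, and its comparator has already been treated.

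**3. Inert drug, drifting background.** Let r1, r2, r3 be the risks in the three quarters. The group ratio at the treatment stage (Group 2 over Group 1) is r1/r2. Each worker contributes one observation to it, so the two-proportion formula approximates its rejection rate. The 20% is the plan's figure; every later or LRI-level risk is an assumption.

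| r1 then r2 | Ratio | Spurious result | 500 per group | 1000 per group |
|---|---|---|---|---|
| 20%, 22% | 0.91 | benefit | 12% | 19% |
| 20%, 25% | 0.80 | benefit | 47% | 76% |
| 20%, 15% | 1.33 | harm | 55% | 84% |
| 10%, 12.5% | 0.80 | benefit | 24% | 42% |

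The nominal rate in one direction is 2.5%. Worked case, 20% then 25% at 500: s0 = 0.02641, s1 = 0.02636, (0.05 − 0.05176)/0.02636 = −0.067, Φ = 47%.

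**4. Interaction, inert drug.** The treatment-stage group ratio over the follow-up-stage group ratio is (r1/r2)/(r2/r3) = r1·r3/r2². Under any constant-ratio trend this is 1: for 20-10-5% it is 0.20 × 0.05/0.10² = 1.00. With a peak of 20-25-20% it is 0.20 × 0.20/0.25² = 0.64.

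**5. True 25% reduction, flat 20%.** The treatment-stage group ratio is 0.15/0.15 = 1.00. The stage term, on over off with no carry-over, is 0.15/0.20 = 0.75. The concurrent months 3-6 pairing reads 0.15/0.20 = 0.75 with no carry-over, 0.15/0.175 = 0.86 with half, and 0.15/0.15 = 1.00 with full.

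**6. The at-least-one-dose rule.** Suppose a fraction f of Group 1's months 0-3 cases never start OM85 and all non-cases do. Group 1's analysed risk becomes 0.2(1 − f)/(0.2(1 − f) + 0.8).
- f = 0.10: 0.18/0.98 = 18.4%. A true ratio of 0.75 reads 0.15/0.184 = 0.82. Power is 30% and 52% at 500 and 1000 per group, against 55% and 84% with all randomised workers.
- f = 0.25: 0.15/0.95 = 15.8%. The ratio reads 0.95 and power is 5% and 7%.

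If cases and non-cases fail to start equally, the factor cancels and the risk stays at 20%.

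**The case against.** The strongest reply is that stage means common periods, months 0-3 and 3-6 in both arms. The first-stage group contrast would then be concurrent and correct (0.15/0.20 = 0.75 in the flat example). The documents do not say this. It would place Group 1's treatment stage before its own treatment-initiation visit, label its on-drug months as follow-up, and drop its months 6-9 although the model runs to follow-up cessation. Figure 1, the study timeline, was not available for this check and could settle the matter.

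A second reply is that Section 13.3 schedules month-3 endpoint analyses and the mixed model covers outcomes measured to follow-up cessation, so concurrent secondary analyses may be intended. That stands as far as it goes. A reader might infer that the plan rules them out; it does not. It gives no model for them.

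Other limits also stand. With flat risk and no carry-over, the stage term does reflect an on/off effect, though as a fixed-order, non-randomised contrast. The interaction is distorted only when the trend is not a constant ratio. The drift and non-start figures are illustrative, and none was computed for symptom days.

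**Conclusion.** The concern holds and should be fixed. Stage has no dates, and on the visit labels no coefficient in the secondary model compares treated with concurrent never-treated workers. False benefit for an inert drug runs from 12% to 47% at 500 per group and from 19% to 76% at 1000 under the assumed rises from 20%. It is 24% and 42% at the assumed LRI-level risks of 10% then 12.5%. These figures rest on the own-clock reading of stage and on assumed later risks.

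A reader might infer that the stage problem also undermines the primary analysis. It does not: that model has no stage term and uses a concurrent window. Nor is the primary a fully safe fallback, because it uses the same dosed-only set, which conditions Group 1 on an act three months after randomisation. That selection is built into the rule. The size and direction of any bias depend on differential non-start, on which the documents give no figure.

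**What to change.** 1. Define the model's time factor from randomisation, with the same windows in both arms.
2. Prespecify months 0-3 as the main between-group comparison for LRI proportions, symptom days and COV ARI/LRI, and name the model. Still report later periods, as supportive for the drug effect.
3. Include all randomised workers in these comparisons and in the primary, whether or not they later take a dose, in place of the rule in 13.2.1.
4. Section 13.2.2 lets the DSMB consider switching Group 1 after the month-1 interim. If that happens, end the main comparison window for proportions, symptom days and the log-rank test at the same time point in both arms.
5. Reconcile Group 2's follow-up cessation, 6 months in Section 10.2 against Day 120 in Appendix 1, before fixing any window.

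The cost is mainly wording, since daily symptom collection starts at day 0 in both arms; workers who never start OM85 must be kept in the dataset. Months 3-9 carry less weight for the drug effect. Power for a 25% LRI reduction at months 0-3 is low: 29% and 51% (500 and 1000 per group) at an assumed 10% risk, and 16% and 28% at 5%. The visit lists and Appendix 1 show no day-0 swab or blood for Group 1, so seroconversion over months 0-3 cannot be established in that arm by rewording; state this as a limitation.

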13.3 Study endpoint assessments

Study endpoint analyses will be conducted 3 months after enrolment and at completion of the study, with an interim analysis planned at month 1.

13.3.1 Primary efficacy endpoint

The primary endpoint, defined in Section 7.2.1, will be analysed 3 months after enrollment using data collected prior to the WLC group commencing treatment, by comparing between-group differences in rates of ARI that necessitated workforce removal. The primary analysis will be conducted using log-binomial regression on both the "intention-to-treat" and "per protocol" groups.

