13.2 Sample size calculations

There are no data in the literature on use of OM85 for the primary prevention of ARI, in relation to COV. However, 20% of Italy's HCW are infected with COV¹. If we assume 20% infection in Gp 1, then with 500 HCW in each group we will be able to detect a reduction in ARI in Gp 2 by 32.5% (to 13.5%) with 80% power ($\alpha=0.05$). Combined with 1000 UK-recruited HCW, we will be able to detect a 25% reduction (80% power, $\alpha=0.05$).

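### If the wait list is switched to OM85 after the month-1 interim, the 3-month primary analysis cannot be done as written, and the plan names no replacement

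*Combined protocol and SAP*

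**What the plan says.** Section 13.2.2 plans an interim analysis of the primary outcome at month 1. If the difference is statistically significant in favour of OM85, "the DSMB will consider immediately switching WLC participants to OM85". The same section then says: "Between-group differences in the primary outcome at 3 months will be assessed using log-binomial regression". Section 13.3.1 places the primary analysis 3 months after enrolment, "using data collected prior to the WLC group commencing treatment".

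Under the normal schedule (section 10.2), Group 1 starts OM85 at its Visit 2, 3 months after randomisation with a window of 5 days either side. Group 2 has its own Visit 2 at the same time with the same window.

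The stopping rules (8.3) and the DSMB section (15.5) do not mention how the primary outcome is analysed after an early switch. The sample size section (13.2) assumes 20% events in Group 1 ("If we assume 20% infection in Gp 1") and states: "Combined with 1000 UK-recruited HCW, we will be able to detect a 25% reduction".

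**The concern.** The two requirements in 13.2.2 and 13.3.1, a comparison at 3 months and only data from before the wait list starts OM85, are compatible if the wait list starts on schedule. After a month-1 switch they are not. Group 1 then has about one month of untreated follow-up, and a 3-month untreated risk cannot be observed.

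The plan provides the switch itself, and the trigger is a favourable result, so the gap opens in the scenario where OM85 appears to work. The planned model compares proportions, with no person-time or offset term mentioned, so nothing in it would correct unequal follow-up. Without a stated rule, the analyst would choose the window knowing the interim result, and the candidate windows give very different answers.

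**Working it through.** **Inputs from the plan (13.2, 13.2.2).** Group 1 risk 20%; 25% reduction, so 15% in Group 2; 1000 per group for both countries combined; alpha 0.05; interim at month 1.

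**Assumptions.** The 20% applies to 3 months (13.2 gives no time window); tests are two-sided; the hazard is constant; OM85 acts at once in switched participants; the interim uses 0.05; everyone has one month of follow-up at the interim.

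**Step 1: the plan's own figures.** With p̄ the mean of p1 and p2, power = Φ{(|p1 − p2| − 1.96·√[2p̄(1 − p̄)/n]) / √[(p1(1 − p1) + p2(1 − p2))/n]}.
- 500 per group, 20% vs 13.5%: (0.065 − 0.0463)/0.0235 = 0.795, power 78.7%. The plan says "by 32.5% (to 13.5%) with 80% power", so this agrees to within rounding.
- 1000 per group, 20% vs 15%: (0.05 − 0.0333)/0.0170 = 0.985, power 83.8%. The stated 25% is slightly conservative for 80% power.

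**Step 2: risks at month 1.** Group 1: 1 − 0.80^(1/3) = 7.17%. Group 2: 1 − 0.85^(1/3) = 5.27%. True 1-month risk ratio: 5.27/7.17 = 0.74.

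**Step 3: chance of meeting the trigger.** The same formula with 7.17% vs 5.27% and n = 1000 gives (0.01895 − 0.02117)/0.01079 = −0.206, so about 42%.

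**Step 4: possible windows after a switch.** If switched at month 1, Group 1's 3-month risk is 1 − 0.80^(1/3) × 0.85^(2/3) = 16.7%. The last two columns come from 400,000 simulated trials, keeping only those with a significant interim in favour of OM85.

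| Window used | Group 1 risk | Group 2 risk | RR, all trials | Median RR, given a switch | Significant, given a switch |
|---|---|---|---|---|---|
| Both groups cut at the switch | 7.2% | 5.3% | 0.74 | about 0.64 | always, for OM85 (by construction) |
| Group 1 cut, Group 2 to 3 months | 7.2% | 15.0% | 2.1 | about 1.9 | over 99.9%, for harm |
| Both to 3 months as randomised | 16.7% | 15.0% | 0.90 | about 0.85 | about a third, for OM85 |

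The true 3-month risk ratio against an untreated control is 0.75 in every row.

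**Step 5: sensitivity to event timing.** The documents give none. If 20% of events fall in month 1, Group 1's month-1 risk is 4%, and the second row's all-trials RR is 15/4 = 3.75. If 50% do, it is 15/10 = 1.5. The direction does not change.

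**Step 6: error rate if the switch-date result counts as primary.** With no true effect, testing at two-sided 0.05 at month 1 (acting only in favour of OM85) and again at month 3 gives an overall error of about 6.9% in simulation. The bivariate normal calculation with one third of the information at the interim gives the same.

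**The case against.** The DSMB is only asked to consider switching, and without an early switch the rule works. Both groups are anchored at 3 months and both have a visit then. That stands, and it makes the point conditional.

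It can also be said that 13.3.1 restricts the data as a whole, not Group 1's data alone, so the natural reading cuts both groups at the same point. That too is fair. But the section does not say so, and the result would not be the 3-month comparison that 13.2.2 requires.

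Four stronger inferences are tempting, and the documents do not support them:
- **The plan as written reverses the result.** The risk ratio near 2 needs the wait list alone to be cut. The wording permits that reading but does not favour it.
- **Diluting the effect with switched controls is one way to follow the text.** It is not: 13.3.1 excludes data from after the wait list starts OM85.
- **A common cut at the switch lowers power from about 84% to about 42%.** The 42% is the chance that the trigger is met. Once it has been met, the result at that cut is already significant, and the problem is exaggeration.
- **The 5-day visit window biases the comparison even without a switch.** Shifting all of Group 1 to Day 85 or Day 95 would give 1 − 0.8^(85/90) = 19.0% or 1 − 0.8^(95/90) = 21.0%. That needs every participant at the same edge. With visits spread evenly the mean stays at 20.0%, and Group 2 has the same window.

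**Conclusion.** The point holds in conditional form. After a month-1 switch the 3-month comparison and the pre-treatment data restriction cannot both be met, and no section says which gives way. This follows from the text and needs no assumption about rates.

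The size is illustrative, resting on the assumptions listed above. On the plan's own effect, the trigger would be met in roughly two trials in five. The same trial could then report an exaggerated benefit, apparent harm or, on an analysis the plan does not allow as primary, a diluted effect. The gap should be closed before the interim is run.

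It is distinct from the choice of interim significance level, since a well-chosen boundary would still leave the window after a switch undefined. The remedy does depend on that level being set.

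**What to change.** In 13.3.1, state that events are counted over the same window in both groups: from randomisation to 3 months or, if the wait list is switched early, to one common data cut-off date set at the switch decision and applied to both groups. For the early-switch case, add that:
- the analysis at the cut-off is primary, and the 3-month as-randomised comparison is supportive;
- the primary result is judged at a pre-specified interim significance level that controls the overall error, for example an alpha-spending boundary;
- the report notes that the estimate is likely to be exaggerated, because the cut was triggered by a favourable result.

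In 13.2.2, define month 1 as per participant or as a calendar date. With the 4-week accrual in the synopsis, these give different amounts of follow-up. Use the same cut-off for the time-to-ARI analysis.

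The cost is a few sentences, a stricter interim threshold and, if a switch occurs, a primary result based on shorter follow-up. Nothing changes in the 3-month window when there is no early switch, and the DSMB's decision on whether to switch is untouched.

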9.1 Inclusion criteria

Participants who meet *all* of the following criteria are eligible for enrolment:

1. HCW in front line clinical departments assessing or caring for patients with suspected or verified COV infection in one of the recruiting hospitals in Brisbane or the UK,
2. Participants who, in the opinion of the investigator, are able to comply with the protocol for its duration,
3. Written informed consent signed and dated according to local regulations.

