13.1 Randomisation, stratification and blinding

Participants will be randomised to the wait list group (Group 1) or the initial intervention group (Group 2) using a one-to-one ratio, stratified by Country (Australia, UK), hospital (QCH, PA, TPC) and department [High risk (ED, ICU, isolation wards), lower risk (radiology, general wards, other)].

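### Randomisation is stratified by country, hospital and department risk, but no planned analysis names these factors; if they are prognostic, a small and free gain in precision is left unused

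*Combined protocol and SAP*

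**What the plan says.** Section 13.1 of the combined protocol and SAP allocates 1:1, "stratified by Country (Australia, UK), hospital (QCH, PA, TPC) and department". Department has two classes: "High risk (ED, ICU, isolation wards), lower risk (radiology, general wards, other").

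The analyses are set out in three places:

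- **Primary endpoint.** Section 13.2.2: "Between-group differences in the primary outcome at 3 months will be assessed using log-binomial regression". Section 13.3.1 repeats the method: "The primary analysis will be conducted using log-binomial regression on both the" intention-to-treat and per-protocol groups. Neither section lists any model term.
- **Secondary and mechanistic endpoints.** Sections 13.2.2 and 13.3.2 specify "mixed-effects models with group and stage (treatment/follow-up) (main effects and interaction) as fixed effects and HCW as random effect". This is the only model whose terms are listed, and the randomisation factors are not among them.
- **Time to event.** Section 13.3.2: "Time-to-ARI, including LRI, analyses will use the log-rank test". No stratification is mentioned.

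Department appears elsewhere only as a breakdown of secondary proportions (Sections 7.2 and 8.2.2). That describes results within departments. It does not adjust the treatment comparison.

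**The concern.** Stratified randomisation balances the arms within strata. If the strata predict the outcome, that balance lowers the true sampling variance of the treatment effect. A log-binomial model with treatment alone does not take this into account. It reports the variance that would apply without stratification, so the confidence interval is a little too wide and the test a little conservative. Putting the strata in the model recovers the difference.

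What is at stake is some precision on the primary risk ratio, plus a primary model whose covariates are fixed in advance. The second matters somewhat here because Sections 10.1.3 and 10.1.4 collect other candidate covariates (medical history, front-line exposure, age, sex, ethnicity, smoking), and the plan does not say which of them, if any, enter the model.

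**Working it through.** **Inputs from the documents (Section 13.2).** Control risk 20%; 25% reduction with both countries combined, so 15% on treatment and a risk ratio (RR) of 0.75; 1000 per group; alpha 0.05, taken as two-sided because the plan does not say; stated power 80%.

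**Assumptions.** The documents give neither risks nor sizes by stratum. I take two strata, a common RR, a two- or three-fold risk gradient, and a high-risk share of 20%, 50%, 80% or 90%. Stratum risks are scaled so that the average control risk stays at 20%.

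**The plan's own figure.** The usual two-proportion formula for 20% against 15% gives 83.8% power at 1000 per group; 80% needs 906 per group. The stated 80% is therefore met with a little to spare.

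**Formulas.** Let w be the stratum share, p the stratum risk in an arm, P the average risk in that arm, and n the number per arm.

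- Reported variance of log RR, treatment only: sum over arms of (1 − P)/(nP).
- True variance under stratified randomisation: sum over arms of [Σ w p(1 − p)]/(nP²).
- Adjusted variance: inverse-variance pooling of the stratum log RRs.
- Power, treatment only: Φ((|log RR| − 1.96 × SE reported)/SE true).
- Power, adjusted: Φ(|log RR|/SE adjusted − 1.96).
- Type I error, treatment only: 2[1 − Φ(1.96 × SE reported/SE true)], with both arms at the control risk.

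**Worked case: equal strata, three-fold gradient (control risks 30% and 10%).**

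- Reported: 0.80/200 + 0.85/150 = 0.00967, SE 0.0983.
- True: (0.105 + 0.045)/40 + (0.0872 + 0.0347)/22.5 = 0.00917, SE 0.0957.
- Adjusted: stratum variances 0.01156 and 0.04267, pooled 1/(86.5 + 23.4) = 0.00909, SE 0.0954.
- |log 0.75| = 0.2877. Power, treatment only: Φ((0.2877 − 0.1927)/0.0957) = Φ(0.992) = 83.9%. Adjusted: Φ(3.017 − 1.96) = Φ(1.057) = 85.5%.
- Type I error: SE reported √0.008 = 0.0894, SE true √0.0075 = 0.0866, so 2[1 − Φ(2.024)] = 4.3%.

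**All cases at 1000 per group.**

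| High-risk share | Gradient | Type I error, treatment only | Power, treatment only | Power, adjusted | Gain (points) |
|---|---|---|---|---|---|
| any | none | 5.0% | 83.3% | 83.3% | 0 |
| 50% | 2-fold | 4.7% | 83.58% | 84.29% | 0.71 |
| 50% | 3-fold | 4.3% | 83.94% | 85.47% | 1.53 |
| 80% | 2-fold | 4.9% | 83.42% | 83.72% | 0.30 |
| 80% | 3-fold | 4.7% | 83.54% | 84.07% | 0.53 |
| 90% | 2-fold | 4.9% | 83.36% | 83.51% | 0.15 |
| 90% | 3-fold | 4.9% | 83.41% | 83.67% | 0.26 |
| 20% | 2-fold | 4.7% | 83.58% | 84.40% | 0.82 |
| 20% | 3-fold | 4.1% | 84.14% | 86.65% | 2.51 |

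**Simulation checks.** With 200,000 trials per scenario and a maximum-likelihood log-binomial fit, the equal-strata three-fold case gave 84.5% against 86.0%, and the 20%-share three-fold case 84.8% against 87.3%. Type I error with strata in the model was 4.9% to 5.0% throughout. A separate simulation with the Mantel-Haenszel risk ratio gave 84.2% against 85.4% for control risks of 30% and 10%. It gave 84.7% against 86.8% for a wider four-stratum spread of 40/20/15/5%, where the unadjusted type I error fell to 3.7%.

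**Cost if the strata are not prognostic.** Eight strata (three equal Brisbane hospitals, one UK level with half the sample, two equal department classes) and no gradient gave power 83.7% against 83.8%, and type I error 4.9% both ways.

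All these figures concern the primary binary comparison, as a single test at 3 months. The log-rank test and the mixed models were compared with the text only.

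**The case against.** **The plan does not say that the primary analysis is unadjusted.** This stands. Sections 13.2.2 and 13.3.1 name a regression and list no terms, not even treatment. The loss arises only if the model is fitted with treatment alone. Stating the covariates settles the question either way.

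**The gain is assumed.** This also stands. Section 13.1 labels one class high risk without giving figures, and the endpoint is any ARI leading to removal from work, not only COV infection. If the strata do not predict it, the gain is zero.

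**The likely stratum mix.** A reader might infer a large high-risk majority from the eligibility rule, "HCW in front line clinical departments assessing or caring for patients with suspected or verified COV infection". The documents do not support that. Sections 6.1.2 and 6.4 count radiology among front-line departments, while Section 13.1 puts radiology, general wards and other departments in the lower-risk class. The shares in the table are plain assumptions.

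**Sparse strata.** With one UK level there are 4 × 2 = 8 strata, on average 1000/8 = 125 participants per arm. The average hides small cells. With half the sample in the UK, three equal Brisbane hospitals and an 80% high-risk share, a lower-risk Brisbane stratum has 500/3 × 0.20 ≈ 33 per arm and about 3 to 4 control events (two-fold) or 2 to 3 (three-fold). This argues for main effects, a non-convergence fallback and pooling in the log-rank test. It does not argue against adjustment.

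**The secondary analyses.** The precision argument does not carry over automatically. For binary outcomes in a mixed model with no stated link, added covariates can change what the treatment coefficient estimates. The mechanistic endpoints are Brisbane only (Synopsis), so country does not apply there.

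**Conclusion.** The point holds as a small, conditional gain in precision. The strata are used to randomise and appear in no planned analysis of the treatment effect. If the primary model contains treatment only, and under the assumed two- to three-fold gradients and shares, about 0.15 to 2.5 points of power are forgone at 1000 per group, and type I error is about 4.1% to 4.9%. With no gradient, both effects vanish. The gain for the log-rank test and the mixed models is not quantified.

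Two stronger readings are tempting and do not follow. First, that ignoring the strata biases the result or inflates the false-positive rate of this comparison: the unadjusted risk ratio is unbiased, and the error is on the conservative side. Second, that the trial falls short of its planned power at 1000 per group for this reason: unadjusted power is at least 83.3% in every case, above the stated 80%. Priority is low.

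**What to change.** - **Primary model.** State that the log-binomial model includes country/hospital and department risk as main effects. Section 13.1 lists hospital levels for Brisbane only, so define the UK as its own level or levels; with a single UK level, country is already contained in hospital. Use modified Poisson regression with robust errors if the model does not converge. Keep the unadjusted risk ratio as a sensitivity analysis. With a common risk ratio across strata, adjustment does not change the quantity estimated.
- **Log-rank test.** Stratify by the same factors, with a rule for pooling sparse strata.
- **Mixed models.** Add the same factors as fixed effects. For the Brisbane-only mechanistic endpoints, use the Brisbane hospital and department factors only. For binary outcomes, state the link and the effect measure.

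The cost is a few SAP sentences, written before outcome data are seen. The factors are already recorded at randomisation, so no new data are needed.
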